2.2 Overview of Proposed Study

This is a pilot RCT (1:1 randomization) of a remote perioperative telemonitoring intervention in major abdominal cancer surgery. We will focus on GI malignancies, because the surgical procedures, extent of resection, and expected surgical outcomes are similar. In Aim 1, we will assess the feasibility, retention, and acceptability of the intervention through statistics of participation, intervention completion (retention) rates, and qualitative data from exit interviews. In Aim 2, surgical outcomes (post-operative complications), healthcare utilization (postoperative complications, hospital readmissions), PROs (symptoms, QOL), and functional recovery (pedometer steps) will be examined by treatment arm. Our primary endpoint is severity (grade) of postoperative complications from discharge to day 30 post-discharge. This study will be conducted in compliance with the protocol, Good Clinical Practice (GCP) and the applicable regulatory requirements.

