Figure 3: Study Schema

Study Procedures

Before Surgery:

The study schema is presented in Figure 3. Patients will be recruited from the surgical clinics at COH's Duarte campus only. Research staff will explain the study purpose, answer questions, and obtain informed consent. Patients will be enrolled at least 3-7 days before surgery. Following informed consent, the study CRA will assist patients with identifying a patient-owned engagement device (smartphone, tablet, computer), and assist with setup and initial testing of the Aetonix application on the device of choice. For patients who do not have an engagement device or have poor connections at home, a study Samsung tablet will be provided for the duration of the study. In our previous experience, only about 1.5% of patients had no device or inadequate internet access.⁴⁸ All patients will be provided with a Vivofit 4 and instructions. The study CRA will setup the device for patients and conduct initial testing to insure successful data transmission. Patients will wear the Vivofit 4 on their non-dominant wrist. Patients in both

arms will receive a package with the Aetonix physiologic PGHD home monitoring devices described previously. The study CRA will provide instructions (both verbal and in writing) on device use. All patients will be instructed to complete baseline assessment (T1) of PGHD and ePROs while at home.

Following completion of baseline assessment, participants will be randomly assigned to either the telemonitoring or enhanced usual care arm, using stratified and blocked randomization. Strata will be defined by diagnosis (upper GI, colorectal, hepatobiliary) and surgical technique (minimally-invasive versus open). Variable block sizes will be used to maintain approximate balance and pre-assignment masking. A pre-established randomization log will be created by the project biostatistician. The study staff will communicate group assignments to the patients.

For patients assigned to the telemonitoring arm, the alert/feedback system, monitored by the CRN, will be initiated for each patient. The system will be triggered on the occurrence of predetermined threshold events for physiologic PGHDs and ePROs, as described previously. Patients assigned to the enhanced usual care arm will use the Aetonix application to report

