13.0 Statistical Considerations

13.1 Study Design

13.1.1 Sample Size Calculation and Power Analysis

We will need 128 patients (64 per arm) to detect an effect size of 0.5 in the primary outcomes as described in Aim 2 (postoperative complications, lower readmission rates, improved symptoms, QOL, and functional recovery) between the two groups, with a two-sided 0.05 significance level using a two-sample t-test and at least 80% power. We will enroll a total of 160 (80 per arm to account for an expectation of 20% attrition. Thus, we will have sufficient power for all primary outcomes, including our primary endpoint of postoperative complications.

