Feasibility will be assessed through: 1) the ratio of eligible participants to those enrolled and those who declines participation; 2) reasons for non-participation; 3) number of scheduled study encounters completed; 3) attrition rate between pre- and post-discharge; 4) reasons for attrition/dropout; 5) the ratio of all participants to those who completed $\geq 70\%$ of the study; These data will be descriptively reported and analyzed. Qualitative data on acceptability from exit interviews will be analyzed using the conventional content analysis approach.⁶⁵ This approach is used to describe a phenomenon where existing theory or research literature is limited. Data from the audio-recorded interviews will be transcribed and analyzed using HyperRESEARCH™ qualitative software. Transcripts will be imported allowing for the development of analytic categories, data coding, and review of coded data. All data will be read repeatedly to achieve immersion and obtain a sense of the whole. Then, data will be read word by word to derive codes. Codes will then be sorted into themes based on links and relationship. Separate investigators ([name] and [name]) will conduct a final validation review of the codes and themes to ensure consistency and clarity across all qualitative data. Data discordantly coded will be discussed for refinement and consensus purposes.

Specific Aim 2: Determine the preliminary efficacy of the remote perioperative telemonitoring intervention on surgical outcomes, healthcare utilization, PROs, and functional recovery.

Hypothesis 2.1: Patients randomized to the telemonitoring arm will experience reduced severity (grade) of postoperative complications, lower readmission rates, and improved symptoms, QOL, and daily steps.

For Specific Aim 2, the primary endpoint is the change in Comprehensive Complications index (CCI) from discharge to day 30 post-discharge. First, change in CCI will be computed. A two-sample t-test will be conducted to determine if there is significant difference between mean CCI of the intervention arm and the control arm. Trends in CCI scores will be explored over time (T2-T5). Exploratory within subjects' correlation will be examined using Pearson correlation between adjacent time points. A random-effects model will be used to study group differences in mean over time. Other variables (e.g., age and sex) may be included in the model to adjust for possible confounding.

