Similar analysis will be carried out for repeatedly measured secondary endpoints (symptom severity score, QOL). Generally speaking, we expect better scores in the intervention arm than the control arm. Healthcare resource use (e.g., hospital readmission) is a secondary endpoint. At each time point, we will estimate the ER visits/readmission rates and provide confidence intervals for each arm. Further, a binomial test for comparing two proportions will be conducted to see if there is significant difference between the readmission rates of the two arms. For simplicity, Bonferroni correction will be used both in the proportions comparisons test and the confidence intervals construction.

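### Randomisation is stratified by diagnosis and surgical technique, but the primary CCI test is unadjusted and no planned analysis names the strata

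*Combined protocol and SAP*

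**What the plan says.** **Design.** Section 5.1 (Study Procedures, Before Surgery) states: "Following completion of baseline assessment, participants will be randomly assigned to either the telemonitoring or enhanced usual care arm, using stratified and blocked randomization". It continues: "Strata will be defined by diagnosis (upper GI, colorectal, hepatobiliary) and surgical technique (minimally-invasive versus open". That makes six strata. Blocks vary in size, and the sizes are not given.

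**Primary analysis.** Section 13.2.1.2, under Specific Aim 2, says: "A two-sample t-test will be conducted to determine if there is significant difference between mean CCI of the intervention arm and the control arm". No stratum or covariate enters this test.

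**Longitudinal analysis.** The same section adds: "A random-effects model will be used to study group differences in mean over time". The adjustment sentence comes next: "Other variables (e.g., age and sex) may be included in the model to adjust for possible confounding". It is permissive, and its position ties it to the random-effects model.

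**Secondary endpoints.** For symptoms and quality of life: "Similar analysis will be carried out for repeatedly measured secondary endpoints (symptom severity score, QOL". Readmissions are compared with a two-proportion test. Diagnosis and technique are not named in any of these analyses.

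**Sample size.** Section 13.1.1 also uses an unadjusted two-sample t-test, with an effect size of 0.5, two-sided 0.05, at least 80% power and 64 per arm. It then says: "We will enroll a total of 160 (80 per arm to account for an expectation of 20% attrition".

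**The concern.** Stratified allocation keeps the arms balanced on diagnosis and technique. If those factors predict CCI, the balance removes between-stratum variation from the arm difference. The t-test's pooled standard deviation still contains that variation, so the reported standard error is larger than the true one. The interval is then too wide and the test runs below its nominal 5%.

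The stakes are limited to the reported standard error, interval and test. They still matter here for two reasons. Section 1.0 says the pilot will supply the effect size for planning a Phase III trial, so the precision reported for the CCI difference is one of its main products. And the open covariate list leaves the choice of adjustment until after the data are seen, while the one set of covariates fixed by the design goes unused.

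**Working it through.** **1. Reproduce the plan's figure.** For a two-sample t-test with d = 0.5, two-sided 0.05 and 80% power, the noncentral t gives 63.77, rounded up to 64 per arm, with power 80.1% at 64. Allowing for attrition, 128 / (1 − 0.20) = 160. Both stated figures are correct.

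**2. Formulas.** Let R² be the share of outcome variance explained by the strata. The documents give no value, so 0 to 0.3 is assumed. In total-SD units, with 64 per arm and balance intact:

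- standard error reported by the t-test: √(2/64) = 0.177, whatever R² is
- true standard error of the difference: 0.177 × √(1 − R²)
- ratio of t-test to adjusted interval width: 1/√(1 − R²)
- true type I error of the t-test: 2 × [1 − Φ(1.96/√(1 − R²))]
- adjusted power: noncentral t on 128 − 2 − 3 = 123 df, noncentrality 0.5 / [0.177 × √(1 − R²)]

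| R² | Width ratio | t-test type I error | Adjusted power |
|---|---|---|---|
| 0 | 1.000 | 5.0% | 80.1% |
| 0.05 | 1.026 | 4.4% | 82.1% |
| 0.1 | 1.054 | 3.9% | 84.1% |
| 0.2 | 1.118 | 2.8% | 88.1% |
| 0.3 | 1.195 | 1.9% | 91.8% |

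**3. Simulation with attrition.** Dropout disturbs the balance, so the formulas overstate the conservatism. The simulation randomises 160 in six strata with 20% random attrition, 12,000 trials per cell. Assumed: blocks of 2, 4 or 6; diagnosis shares 25/40/35%; minimally-invasive shares 50/60/35%; additive stratum effects; normal outcome; d = 0.5 in total-SD units. Monte Carlo error is about 0.2 point for type I error and 0.4 for power.

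| R² | Type I error, t-test v adjusted | Width ratio | Power, t-test v adjusted |
|---|---|---|---|
| 0 | 5.1% v 5.1% | 1.00 | 80.0% v 79.7% |
| 0.05 | 4.5% v 4.9% | 1.02 | 80.9% v 82.1% |
| 0.1 | 4.3% v 5.2% | 1.05 | 81.1% v 83.9% |
| 0.2 | 3.3% v 5.0% | 1.12 | 81.8% v 87.6% |
| 0.3 | 2.7% v 5.3% | 1.19 | 83.4% v 91.8% |

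The t-test's mean reported standard error was 0.177 in every row. The actual SD of its estimate fell from 0.178 at R² = 0 to 0.170 at 0.1 and 0.155 at 0.3. The adjusted estimate's SD was 0.179, 0.169 and 0.149. So most of the precision is already in the unadjusted estimate, and the t-test fails to report it.

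**4. Sensitivity to the assumptions.** A second simulation used other stratum shares and effects, blocks of 2 and 4, and 10,000 trials per setting. At R² = 0.1 it gave type I error 4.1% v 4.9% and power 81.3% v 83.9%. At R² = 0.3 it gave 2.5% v 4.8% and 83.0% v 91.0%.

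**5. A CCI-like score.** CCI runs from 0 to 100 and many patients will score 0. A zero-inflated score was simulated with 34% having any complication, near the one third cited in Section 1.0, and assumed stratum rates of 20% to 55%. R² was then only about 0.04. Type I error was 4.4% unadjusted v 4.7% adjusted, and the reported standard errors differed by a ratio of 1.017. For three assumed effects on such a score, power was 51.8% v 52.3%, 70.0% v 71.2%, and 77.7% v 78.4%. The linear model holds its level, and the gain is about one point.

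**The case against.** The case against is that nothing here is an error. The t-test is valid, it protects type I error, the planned power is met, and the point estimate hardly moves. For a pilot of preliminary efficacy, a simple and mildly conservative test is defensible. All of that stands.

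The larger gains also lack support in the documents. Section 2.2 justifies the GI focus "because the surgical procedures, extent of resection, and expected surgical outcomes are similar", which points to a low R². If stratum differences act only through the rate of any complication, with about 34% affected, R² = 0.2 would need two equal halves with rates near 13% and 55%: 0.21² / (0.34 × 0.66) = 0.20. R² = 0.3 would need about 8% and 60%: 0.26² / 0.2244 = 0.30. Varying severity would require still wider gaps. Section 13.2.1.2 also defines the endpoint as a change from discharge, which may remove some stratum-related morbidity, and none of the simulations models a change score. This stands too, and it makes 0 to 0.1 the range to plan on.

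A further argument is that the covariate list is open, so the strata could be added later. That does not reach the primary t-test, and leaving the choice open is part of the problem.

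None of this argues for ignoring the strata. The plan chose these two factors for randomisation, and the adjusted analysis costs almost nothing if they turn out not to matter.

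**Conclusion.** The concern holds. The design stratifies by diagnosis and technique, the primary CCI test ignores both, and no planned analysis names them. This is lost efficiency and incomplete pre-specification; it is not a threat to validity. The sample size needs no change.

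The size depends on an R² that the documents do not give. At 0.05 to 0.1, intervals are 2% to 5% too wide and 1 to 3 power points are lost. At 0.2 to 0.3, which should be read as hypothetical, intervals are 12% to 19% too wide and 6 to 8 points are lost. At 0 there is no loss. On a zero-inflated CCI-like score the gain was about one point. The change should be made because it is nearly free, although the likely gain is small.

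**What to change.** - **Primary test.** In Section 13.2.1.2, replace the two-sample t-test with a linear model of the CCI endpoint on arm, diagnosis and surgical technique. Report the arm difference with its 95% interval, and keep the t-test as a sensitivity analysis. The replacement works whichever CCI definition and visit numbering the plan settles on.
- **Which values.** Use diagnosis and technique as recorded at randomisation. Section 11.1 also collects the operative technique, which can differ from the plan and is known only after allocation.
- **Other models.** Put the same two factors in the random-effects models for CCI, symptoms and quality of life. Age and sex can stay as exploratory terms. For consistency, a stratified or adjusted comparison can be given for readmissions.
- **Stratum definition.** Section 3.1 admits cytoreductive surgery for peritoneal carcinomatosis, which has no evident place among the three diagnosis strata. State which stratum these patients enter, so that the model factor is defined for everyone.

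**Cost.** One or two sentences for the primary model and a few words for the rest. No new data and no change in sample size. The model uses three more degrees of freedom (126 to 123 at 64 per arm). If the strata explain nothing, the power cost is about 0.1 point by formula and 0.3 point in simulation, the latter within Monte Carlo error.

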3.1.2 Age Criteria, Performance Status and Life Expectancy

Age criterion for this study is based on the NIH's age criteria, which defines an adult as individuals aged 18 years and over. There are no restrictions related to performance status or life expectancy.

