11.0 Endpoint Evaluation Criteria/Measurement of Effect

11.1 Response Criteria

Outcome Measures – Outcomes are assessed before surgery (baseline), before discharge, and until 30 days post-discharge (**Table 1**). Measures were selected based on reliability/validity, our preliminary studies, and brevity to minimize burden. ePROs will take about 4-7 minutes to complete. We will also obtain sociodemographic, clinical (diagnosis, tumor stage, neoadjuvant treatments, Charlson-Deyo co-morbidity index, time to adjuvant treatment), and surgical (Pre-op ECOG performance score, procedure, open or minimally invasive, ASA classification, date of surgery, post-op admission status and date, ICU days, post-operative events, discharge date, discharge status) data for all patients.

Table 1. Outcome Measures by Aims and Assessment Time Points

	Measures	Before Surgery (T1)	Pre-Discharge (T2)	Day 2 (T3)	Day 7 (T4)	Day 14 (T5)	Day 30 (T6)
SA 1 (Feasibility, Retention and Acceptability)	Participation Rate - % of eligible consented, reasons for non-participation, dropout and lost to follow-up rates, reasons for dropout, differential dropout by treatment arm.						Throughout study period
	Telemonitoring Completion Rate – number of PGHD and ePRO assessments completed ($\geq 70\%$)						Throughout study period
	Patient Experience – Semi-Structured Exit Interview Guide						X
SA 2 (Preliminary Efficacy)	Post-Operative Complications – Comprehensive Complications Index (CCI) ^{131, 132}		X	X	X	X	X
	Hospital Readmissions				X	X	X
	General Symptoms - MD Anderson Symptom Inventory (MDASI) ^{55, 120}	X	X	X	X	X	X
	Disease-Specific Symptoms – MDASI Symptom Library	X	X	X	X	X	X
	QOL – EQ-5D-5L ^{10,113,121-125}	X	X	X	X	X	X
	Functional Activity (daily steps taken) ¹²⁷⁻¹³⁰						Throughout study period

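### Preoperative risk measures collected for every patient are named in no inferential Aim 2 analysis, and the covariate clause for the longitudinal models is open-ended

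*Combined protocol and SAP*

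**What the plan says.** **What is collected.** Section 11.1 lists data to be obtained for all patients. It includes the Charlson-Deyo index and "Pre-op ECOG performance score, procedure, open or minimally invasive, ASA classification". The same list goes on to "ICU days, post-operative events, discharge date, discharge status".

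**Who is enrolled.** Section 3.1.1 takes all disease stages, and section 3.1.2 adds: "There are no restrictions related to performance status or life expectancy".

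**How patients are randomised.** Section 5.1 (Study Procedures, Before Surgery) randomises after the baseline assessment and before surgery. The strata are diagnosis (three levels) and surgical technique (two levels).

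**How Aim 2 is analysed.** Section 13.2.1.2 computes the change in CCI from discharge to day 30 and compares arms with a two-sample t-test without covariates. It then describes a random-effects model for group means over time, followed by the only covariate rule in the plan: "Other variables (e.g., age and sex) may be included in the model to adjust for possible confounding". Symptom severity and quality of life are to be analysed in a similar way. Readmission is compared as two proportions.

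**How the trial was sized.** Section 13.1.1: "We will need 128 patients (64 per arm) to detect an effect size of 0.5", "with a two-sided 0.05 significance level using a two-sample t-test and at least 80% power".

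**The concern.** Two separate matters arise from the same short stretch of section 13.2.1.2.

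The first is precision. Eligibility is broad, so comorbidity, performance status and ASA class plausibly explain some of the variation in complications. They are already collected, but the primary test does not use them. Whatever they explain stays in the error term, and chance imbalance in them is controlled neither by the strata nor by the analysis.

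The second is the freedom left in the longitudinal models. The clause is optional, gives examples rather than a list, has no selection rule and sets no time limit on what may be a covariate. Covariates could be chosen after results are seen. A variable affected by the intervention could also be adjusted for: telemonitoring begins before surgery (section 1.0), and post-operative events overlap with what the CCI measures. This matters because section 1.0 says the findings will supply the effect size for a later Phase III trial.

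**Working it through.** **1. The plan's own figure.** Inputs from section 13.1.1: standardised effect 0.5, two-sided 0.05, two-sample t-test, 80% power, 20% attrition.

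- Non-centrality at 64 per arm: 0.5 × √(64/2) = 2.828. With 126 degrees of freedom and critical value 1.979, power is 80.1%.
- Solving for 80% power gives 63.77, so 64 per arm and 128 in total. Then 128 / (1 − 0.20) = 160.

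The stated 128 and 160 reproduce.

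**2. What adjustment could add.** If the covariates explain a share R² of the outcome variance, the residual SD shrinks by √(1 − R²) and the non-centrality becomes 2.828 / √(1 − R²). The documents give neither R² nor an SD for the CCI, so R² is an assumption and is shown as a range. This ideal calculation ignores the cost of estimating the covariate effects.

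**3. Charging for the covariates.** With N = 128 and k covariate terms, chance imbalance inflates the variance of the arm effect on average by about (N − 3)/(N − k − 3), and the degrees of freedom fall to N − 2 − k. For k = 4 (age, Charlson-Deyo, ECOG, ASA, one term each) the inflation is 125/121 = 1.033. The non-centrality is multiplied by √(121/125) = 0.984, with 122 degrees of freedom.

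| Assumed R² | Power, ideal | Power, k = 4 | Equivalent unadjusted N (ideal), 128/(1 − R²) |
|---|---|---|---|
| 0 | 80.1% | about 79% | 128 |
| 0.05 | 82.1% | about 81% | 135 |
| 0.10 | 84.1% | about 83% | 142 |
| 0.20 | 88.1% | about 87% | 160 |
| 0.30 | 91.9% | about 91% | 183 |

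Break-even with the unadjusted test is near R² = 1 − 121/125 = 0.032.

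The strata add (3 − 1) + (2 − 1) = 3 terms. Blocking within strata keeps them nearly balanced, so their cost is close to the degrees of freedom alone. As a pessimistic bound, treat all seven terms as unbalanced, with factor √(118/125) and 119 degrees of freedom. Power is then about 78%, 80%, 82%, 86% and 90% over the same R² values, with break-even near 1 − 118/125 = 0.056.

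**4. What an open list could do in an adjusted model.** As a worst case, 3,000 null trials of 128 patients were simulated with 3 or 5 independent prognostic covariates, keeping the smallest p-value over all covariate subsets. Type I error at nominal 5%:

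| Covariates | Total R² 0.10 | 0.20 | 0.30 |
|---|---|---|---|
| 3 | 8.5% | 9.7% | 11.1% |
| 5 | 9.0% | 11.9% | 13.8% |

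The unadjusted test in the same simulations stayed between 4.7% and 5.7%. These are single-outcome linear models. They illustrate the risk from the clause and say nothing about the fixed t-test.

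**5. Timing of candidate covariates.** Set section 11.1 beside section 5.1. ICU days, post-operative events, discharge date and discharge status all follow surgery, hence follow randomisation, and the clause does not exclude them. For ASA class and preoperative ECOG, section 11.1 does not say whether they are recorded before or after randomisation.

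**The case against.** The case on the other side is substantial, and most of it limits the point rather than removing it.

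- **The unadjusted test is legitimate.** Randomisation makes it valid, the sample size was planned for it, and this is a pilot of preliminary efficacy. A reader might infer that the trial is underpowered. The documents do not support that: the stated power reproduces.
- **The primary result is not exposed to the clause.** A reader might infer that the main CCI result could be over-adjusted or chosen from several covariate sets. It could not. The t-test has no covariates, and the clause refers to the random-effects model that precedes it.
- **The risk measures are not unused.** A reader might infer that they enter no analysis. Section 13.2.1.2 summarises all variables descriptively, section 13.2.1.1 may draw on other variables when examining missing data, and the open clause could admit them. The accurate statement is that no inferential Aim 2 analysis names them.
- **Post-randomisation adjustment is possible, not proposed.** The clause gives confounding as its purpose, and both its examples are baseline variables. That restrains the choice loosely, but it is not an exclusion.
- **R² is unknown and may be low.** Complications before discharge are already in the discharge value, so preoperative risk may explain less of a change in CCI after discharge than of total complications. This stands, and is why the range starts at zero.
- **An adjusted model for readmission is not shown to be supportable.** The documents give no readmission rate from which to judge a multi-covariate logistic model at about 128 evaluable patients. This stands too.

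**Conclusion.** The point holds in two limited parts.

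First, the primary analysis is sound but forgoes precision that already-collected data might provide. With four covariate terms the change in power runs from a loss of about one point at R² = 0 to a gain of about eleven points at R² = 0.30. Adjustment helps once R² exceeds roughly 0.03 to 0.06. These figures assume 64 evaluable patients per arm, an effect of 0.5 SD and a linear model. The R² values are not from the documents.

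Second, the covariate clause leaves the random-effects model for CCI, and the similar models for symptoms and quality of life, open to selection after results are seen and to adjustment for consequences of surgery. The simulated error rates of about 8.5% to 14% are a worst case, not a forecast.

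The trial remains valid without the change. It is still worth making, because the possible gain is useful and the cost is small.

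**What to change.** Replace the covariate sentence in section 13.2.1.2 with a rule to this effect:

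- **Primary CCI comparison:** a linear model with arm, the two stratification factors (diagnosis and technique, as recorded at randomisation) and a closed list: age, Charlson-Deyo index, and preoperative ECOG and ASA class each as a single ordinal term. ECOG and ASA enter only if recorded before randomisation, so the plan should state when they are recorded. The unadjusted t-test is reported as supportive.
- **Random-effects models for CCI, symptoms and quality of life:** the same list.
- **Exclusion:** no variable measured after randomisation may be a covariate.
- **Anything else:** any other adjustment is labelled exploratory.
- **Readmission:** leave the comparison of proportions as planned.

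The cost is SAP wording, with no new data, patients or visits. The downsides are a few degrees of freedom (about one point of power if the four covariates are not prognostic) and a main estimate that is reported as covariate-adjusted.

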The **primary objective** of this proposal is to conduct a pilot randomized trial of a remote, perioperative telemonitoring intervention to improve patient-centered outcomes, surgical outcomes, and healthcare resource use in English and Spanish-speaking patients scheduled to undergo major abdominal gastrointestinal (GI) cancer surgery. The intervention includes: 1) objective, device monitoring of physiologic parameters (temperature, blood pressure, heart rate, pulse oximetry, weight); 2) objective, wristband pedometer monitoring of functional activity (daily steps taken); 3) ePROs (symptoms, QOL); and 4) a real-time, alert/feedback system. Telemonitoring will begin before surgery, during hospitalization, and end at 30 days post-discharge. The feedback system is triggered by deviations from predetermined clinical thresholds, and results in telehealth nursing assessment, triage, and management. Our **central hypothesis** is that remote telemonitoring of PGHD and ePROs are feasible and acceptable to patients, and will enhance surgical outcomes, reduce undesirable healthcare utilization, and improve PROs compared to the enhanced usual care condition. We will test our central hypothesis and accomplish our overall objective by pursuing the following **specific aims**:

Specific Aim 1: Assess the feasibility, retention, and acceptability of the remote perioperative telemonitoring intervention as measured by the percentage of patients who a) agree to participate; b) complete $\geq 70\%$ of the telemonitoring; and c) report satisfaction with the intervention through structured exit interviews.

Specific Aim 2: Determine the preliminary efficacy of the remote perioperative telemonitoring intervention on surgical outcomes, healthcare utilization, PROs, and functional recovery.

Hypothesis 2.1: Patients randomized to the telemonitoring arm will experience reduced severity (grade) of postoperative complications, lower readmission rates, and improved symptoms, QOL, and daily steps.

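### Symptoms and QOL have no stated reference visit: read literally, change runs from pre-discharge, after randomisation, and the pre-randomisation T1 score has no specified role in comparing the arms

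*Combined protocol and SAP*

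**What the plan says.** The between-arm plan for symptoms and QOL is one sentence in Section 13.2.1.2: "Similar analysis will be carried out for repeatedly measured secondary endpoints (symptom severity score, QOL"). It names no reference visit, change score or covariate of its own.

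The analysis it refers to is the one for CCI, in the preceding paragraph of the same section:
- change in CCI from discharge to day 30 is computed, and the arms are compared by a two-sample t-test;
- "Trends in CCI scores will be explored over time (T2-T5");
- a random-effects model compares group means over time;
- other variables may be added, with age and sex as the examples.

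The timing of the patient-reported measures is given elsewhere:
- Section 5.1 (Before Surgery): "All patients will be instructed to complete baseline assessment (T1) of PGHD and ePROs while at home". Randomisation follows completion of that baseline.
- Section 1.0: "Telemonitoring will begin before surgery, during hospitalization, and end at 30 days post-discharge".
- Section 5.1 (After Surgery and Before Hospital Discharge): the electronic PROs are repeated before discharge, as T2.
- Section 10.0 and Table 1 in Section 11.1: MDASI and EQ-5D-5L are scheduled at T1, pre-discharge and every post-discharge visit. CCI starts only at pre-discharge.

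Visit labels here follow Section 13.2.1.2 (T2 pre-discharge, T5 day 30). The study calendar and Table 1 add a day-2 visit, so that day 30 is T6.

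**The concern.** A discharge start is understandable for CCI, which has no preoperative value. That reason does not carry over to MDASI and EQ-5D-5L, which are measured before surgery and before randomisation. T1 is the only patient-reported value that the assigned arm cannot have influenced. T2 is a post-randomisation measurement, taken after the intervention is said to have started.

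If T2 is used as the baseline of a change score, any benefit or harm present by discharge is removed from the estimate. Meanwhile the measurement suited to baseline adjustment has no prespecified use in comparing the arms.

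Hypothesis 2.1 claims improved symptoms and QOL. Sections 13.1.1 and 13.2.1.2 count both among the primary outcomes, although the last paragraph of 13.2.1.2 calls them secondary endpoints. Section 1.0 also says the trial will supply the effect size for a Phase III design, so an ambiguous reference visit would carry into that calculation.

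**Working it through.** **1. The plan's own figure.** Section 13.1.1: "We will need 128 patients (64 per arm) to detect an effect size of 0.5 in the primary outcomes as described in Aim 2", "with a two-sided 0.05 significance level using a two-sample t-test and at least 80% power". An exact two-sample t-test with d = 0.5 needs 63.8, so 64 per arm, with power 80.1%. Enrolment: "We will enroll a total of 160 (80 per arm to account for an expectation of 20% attrition"; 128 / (1 − 0.20) = 160. Both figures reproduce. The rest uses 64 per arm.

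**2. Assumptions not in the documents.** SD is 1 at every visit and the true day-30 difference is 0.5 SD. Let e be the arm difference already present at T2, ρ the T2-day 30 correlation and r the T1-day 30 correlation. The documents give no value for e, ρ or r, so ranges are shown. All power figures are for a two-sided 0.05 t-test.

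**3. Change from T2 to day 30.** Expected difference = 0.5 − e. Variance = 2(1 − ρ), which is 1.4, 1.0 and 0.6 for ρ = 0.3, 0.5 and 0.7. Standardised effect = (0.5 − e) / √(2(1 − ρ)).

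| e | ρ = 0.3 | ρ = 0.5 | ρ = 0.7 |
|---|---|---|---|
| 0 | 0.5/√1.4 = 0.423; 66.0% | 0.5/√1.0 = 0.500; 80.1% | 0.5/√0.6 = 0.645; 95.2% |
| 0.1 | 0.338; 47.5% | 0.400; 61.2% | 0.516; 82.6% |
| 0.2 | 0.254; 29.6% | 0.300; 39.1% | 0.387; 58.5% |

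**4. Day-30 score adjusted for T1.** Because T1 precedes randomisation, the expected difference is 0.5 whatever e is. Residual variance = 1 − r². Standardised effect = 0.5 / √(1 − r²). The single degree of freedom for the covariate is ignored.

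| r | Residual variance | Effect | Power |
|---|---|---|---|
| 0.3 | 0.91 | 0.524 | 83.7% |
| 0.5 | 0.75 | 0.577 | 90.0% |
| 0.7 | 0.51 | 0.700 | 97.6% |

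**5. Random-effects model on score levels.** Take the four visits of Section 13.2.1.2 from T2 on, equally weighted, with difference e at T2 and 0.5 at each later visit. The average difference is (e + 3 × 0.5)/4, which is 0.375, 0.425 and 0.500 for e = 0, 0.2 and 0.5. A difference at T2 adds to this estimate and is not subtracted from it.

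**The case against.** Four objections deserve weight.

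- **Discharge is not declared as the baseline for these endpoints.** A reader might infer that the plan fixes it. The text says only that the analysis is similar. The T2 start was written for CCI, and Section 13.2.1.2 itself labels T1 as baseline. Even the t-test sentence speaks of mean CCI and not mean change. This stands: discharge is the literal reading, but the firm defect is that no reference visit is stated.
- **T1 is not wholly unused.** Section 13.2.1.2 summarises all variables descriptively, and its covariate examples do not exclude T1. This also stands. What is missing is a specified role in comparing the arms.
- **The subtraction does not affect the whole plan.** It applies to the change-score t-test. As step 5 shows, the model on means retains a T2 difference.
- **An early effect is not shown.** No PRO assessment is scheduled between T1 and T2, the weight alert is relative to discharge, and daily vital signs are described after discharge (Section 5.1). Only steps are recorded throughout. The effect at T2 may be small or zero.

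Two further inferences are tempting and unsupported. One is that discharge is the symptom low point: Section 2.4 reports QOL worsening at discharge and at day 5, and puts the highest symptom severity at day 5. The other is that the change score mostly reflects the patient's state at discharge: with equal SDs, T2 explains (1 − ρ)/2 of its variance, which is 35%, 25% or 15% for ρ = 0.3, 0.5 or 0.7.

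None of this supplies a stated reference visit or a prespecified use of T1.

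**Conclusion.** The point holds in a limited form. The PRO analysis is defined only by reference to the CCI analysis. Its literal reading takes change from a post-randomisation visit, and the pre-randomisation score has no specified role in the between-arm comparison.

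The documents do not support saying that any benefit by discharge will be lost. That would need both an effect at T2 and reliance on the change-score test. If e = 0 there is no bias and the question is precision, which can go either way. Change from T2 at ρ = 0.7 (95.2%) exceeds T1 adjustment at r = 0.5 (90.0%), whereas at a common correlation of 0.3, 0.5 or 0.7 T1 adjustment is better. If 0.2 SD is present at T2, power for the change score falls to between 29.6% and 58.5% over the range shown, while the T1-adjusted contrast is unaffected.

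These figures illustrate the mechanism under assumed SDs, correlations and early effects; they do not predict this trial's power. The stated sample size reproduces and does not need to change. The SAP should be amended, because the better analysis uses data already scheduled.

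**What to change.** In Section 13.2.1.2, replace the sentence that carries the CCI analysis over to symptoms and QOL with text such as:

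> MDASI and EQ-5D-5L scores at the pre-discharge visit and all post-discharge visits will be compared between arms in a random-effects model, with the T1 (pre-surgery) score as a prespecified covariate. The pre-discharge visit is an outcome visit and not a baseline. The main contrast is the between-arm difference at day 30, adjusted for T1.

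A T1-adjusted average over the post-discharge visits would also serve Hypothesis 2.1; what matters is that one contrast is named in advance. Identify visits by name or day, because the labels in Section 13.2.1.2 differ from those in Section 10.0 and Table 1.

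The cost is SAP wording only. T1 is already scheduled for every patient before randomisation, so no new data, visits or sample-size change are needed.
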